10.2.5 Postoperative Period - 48 hours (Visit 5)

- Opioid consumption
- Pain scores (CPOT, NRS) q 4 hours
- Time until first rescue opioid analgesia
- Time until return of bowel function
- CAM-ICU q 8-12 hours

10.2.6 Postoperative Period - 72 hours (Visit 6)

- Opioid consumption
- Pain scores (CPOT, NRS) q 4 hours
- Time until first rescue opioid analgesia
- Time until return of bowel function
- CAM-ICU q 8-12 hours

- Hospital length of stay

10.2.7 Follow Up - 90 days after DOS (phone)

- Standardized pain questionnaire (Brief Pain Inventory Short Form)

Study Activities

1. Surgery clinic education form explaining the study will be provided to the patient.
2. Anesthesia schedule will be screened by a member of the research team at least one week in advance to identify prospective study participants.
3. One of the study team members will call the patient prior to the day of surgery, confirm eligibility to participate, explain the study, review the study materials and obtain verbal consent from patient prior to the DOS.
4. Prospective patients will be added to Anesthesia Block List with a note about the study after written consent is obtained from the patient.
5. On the day of surgery, the patient will proceed through the usual preoperative process. A member of the study team will meet the patient, evaluate the patient for interval changes in their health, and obtain written informed consent to participate in the study.
6. Randomization will occur the morning of surgery. The patient will be randomized to receive 15mL of 0.25% bupivacaine with 10mL of liposomal bupivacaine bilaterally vs 25mL saline bilaterally within the pecto-intercostal fascial plane.
7. The block team will perform ultrasound-guided bilateral single-shot PIFBs with 0.25% bupivacaine plus liposomal bupivacaine versus saline after induction of general anesthesia in the operating room.
8. The patient, in-room anesthesia team, surgical team, and ICU team will be blinded to randomization status. The block team will not be blinded given the need to draw-up medications immediately prior to block placement and the distinct sonographic appearance of liposomal bupivacaine. The medication syringe will be covered by a towel after being drawn up and during injection to prevent blinded parties from visualizing the contents being injected. The ultrasound will also be turned such that only the anesthesiologist performing the procedure can see.
9. All patients participating in the study will receive wrist bands indicating the possible use of liposomal bupivacaine to avoid additional local anesthetic or regional intervention for at least 96 hours following the nerve block or sham procedure.
10. All patients participating in the study will receive a standardized intraoperative analgesic protocol according to our local institutional cardiac ERAS protocol.
11. A member of the anesthesia block team (who was not involved in the block procedure) will see the patient on postoperative day (POD) 1 to monitor for any complications of the block.
12. The remainder of data collection will occur electronically.
13. A member of the research team will call the patient 90 days after surgery to administer a Brief Pain Inventory Short Form.
14. All medications taken for analgesia at home regularly, prior to arrival on the day of surgery, and perioperatively (until 72 hours postoperatively) will be recorded.

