6.0 STUDY OBJECTIVES AND ENDPOINTS

Objectives	Endpoints

Primary
 
To evaluate postoperative opioid requirement within 72 hours in patients who received local anesthetics via PIFB compared to those control patients who received saline.
	
Total opioid consumption during the initial 72 hours postoperatively will be measured in morphine equivalents and compared between groups.

Secondary
 
 • To evaluate intraoperative opioid consumption in patients who received local anesthetics via PIFB compared to those control patients who received saline. • To evaluate intensity of postoperative pain in patients who received local anesthetics via PIFB compared to those control patients who received saline. 	
 • Total intraoperative opioid consumption will be measured in morphine equivalents and compared between groups. • Pain will be assessed, according to standard of care, every 4 hours using the 11-point Numerical Rating Scale (NRS), beginning at time 0 (arrival to ICU). Each patient's pain scores within each postoperative day will be averaged, and the mean pain scores during each day and throughout the first 72 hours will be compared between the intervention and control groups. Maximum pain scores will also be compared between groups. Pain

	
at 90 days postoperative will be surveyed by phone.
 
 • To evaluate daily postoperative opioid consumption within 72 hours in patients who received local anesthetics via PIFB compared to those control patients who received saline.

 • To evaluate duration of mechanical ventilation in patients who received local anesthetics via PIFB compared to those control patients who received saline. 	
 • Duration of mechanical ventilation will be measured by hours of mechanical ventilation after admission to the ICU.

 • To evaluate return of bowel function in patients who received local anesthetics via PIFB compared to those control patients who received saline. 	
 • Return of bowel function will be measured in the number of postoperative days until the first bowel movement.

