9.0 PROCEDURAL INTERVENTION

9.1 Study Procedural Intervention(s) Description

The intervention portion of this study is the randomized assignment (1:1) to receive 25mL of saline or 15mL of 0.25% bupivacaine mixed with 10mL of liposomal bupivacaine (133mg) as a single-shot injection into the pecto-intercostal fascial plane bilaterally. All studied volumes are well within the acceptable range for pecto-intercostal nerve blocks described previously. All patients will be treated intraoperatively according to our institutional enhanced recovery after surgery for cardiac patients, including the use of dexmedetomidine and ketamine infusions with as-needed fentanyl intravenous dosing.

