9.2 Method for Assigning to Treatment Groups

After consent is obtained, participants will be randomized to an intervention group. Randomization will be accomplished using an online service (www.randomizer.org) and prefilling sealed envelopes determining each subject's intervention group. Randomization will occur immediately prior to the intervention. All subjects will receive the standard of anesthesia care appropriate for their surgery or procedure as determined by the primary anesthesia team caring for the subject, regardless of randomization group. Each study subject as well as the OR anesthesia team, cardiac surgery team, cardiothoracic ICU team, and nursing staff caring for the patient will be blinded to the study drug the patient received. However, the anesthesia provider performing the block (separate from the provider caring for the patient in the operating room) will not be blinded to the study drug injected and will have access to all monitors deemed appropriate by the primary team caring for the subject. In order to maintain blinding during the procedure, the medication syringe will be covered by a towel after being drawn up and during injection to prevent the intraoperative teams from visualizing the contents being injected. The ultrasound will also be turned such that only the anesthesiologist performing the procedure can see, as Exparel has a distinct sonographic appearance on injection. Specific individuals who were involved in the block placement will not perform any follow-up assessments or evaluations of the study patients for the remainder of the study.

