10.2.2 Intra-operative Period (Visit 2)

- Surgery length
- Intraoperative opioid consumption
- ASA Status

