12.0 STUDY ANALYSIS

12.1 Statistical Hypotheses

12.1.1 Primary Efficacy Endpoint(s):

Patients who receive local anesthetic via PIFB will demonstrate lower total opioid use during the initial 72 hours postoperatively compared to patients in the sham-control group.

12.1.2 Secondary Efficacy Endpoint(s):

- Patients who receive local anesthetic via PIFB will have a decreased intraoperative opioid requirement compared to patients in the saline-control group.
- Patients who receive local anesthetic via PIFB will have lower maximum and mean pain scores during the first 72 hours postoperatively and at 90 days postoperatively compared to patients in the saline-control group.
- Patients who receive local anesthetic via PIFB will demonstrate lower daily opioid use during the initial 72 hours postoperatively compared to patients in the sham-control group.
- Patients who receive local anesthetic via PIFB will demonstrate a significant reduction in time to extubation compared to patients in the saline-control group.
- Patients who receive local anesthetic via PIFB will demonstrate a significantly decreased time to return of bowel function compared to patients in the saline-control group.
- Patients who receive local anesthetic via PIFB will demonstrate a significantly reduced rate of postoperative delirium compared to patients in the saline-control group.
- Patients who receive local anesthetic via PIFB will demonstrate a significantly decreased ICU length of stay compared to patients in the saline-control group.
- Patients who receive local anesthetic via PIFB will demonstrate a significantly decreased hospital length of stay compared to patients in the saline-control group.
- Patients who receive local anesthetic via PIFB will demonstrate a significantly decreased persistent use of opioids at 90 days postoperatively compared to patients in the saline-control group.

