12.4 Statistical Methods

The primary endpoint is total postoperative opioid requirement within 72 hours. Total opioid requirement will be measured in morphine equivalents, presented as mean +/- standard deviation, and compared between study groups using a two-tailed independent samples t-test. Secondary outcomes (total intraoperative opioid requirement, mean and maximum 72-hour postoperative pain scores, and pain score 90 days postoperatively) will also be presented as mean +/- standard deviation and compared using independent samples t-tests. Daily postoperative opioid use and mean pain scores on POD1, POD2, and POD3 will also be compared separately with Holm-Bonferroni correction. For pain scores, we will compare mean VRS and average each patient's score within each day before averaging across days. We recognize the debate in the literature about how to analyze pain scores. In the previously referenced randomized controlled trials^{19,20}, the authors used mean scores so we will do so as well.

Continuous secondary outcomes that we expect will not be approximately normally distributed (duration of mechanical ventilation, time until return of bowel function, ICU length of stay, hospital length of stay) will be presented as median with interquartile range and compared using Mann-Whitney tests. Categorical variables (delirium, chronic opioid use) will be presented as counts or as percentages and will be compared using Fisher's exact test. For all planned comparisons with parametric tests, non-parametric equivalents will be substituted if the assumptions of parametric testing are found to be violated before testing.

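### The intraoperative opioid endpoint has no start time although the block follows induction, so any opioid given before the block would be counted in an outcome meant to show its effect

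*Combined protocol and SAP*

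**What the plan says.** Sections 3.1 and 6.0 define the first secondary endpoint in one sentence: "Total intraoperative opioid consumption will be measured in morphine equivalents and compared between groups". The Visit 2 data list (Section 10.2.2) has a single undivided item, "Intraoperative opioid consumption". It lists surgery length but no block time. Section 12.1.2 states the hypothesis that block patients "will have a decreased intraoperative opioid requirement compared to patients in the saline-control group". Section 12.4 says that this and the related secondary outcomes "will also be presented as mean +/- standard deviation and compared using independent samples t-tests", with no covariate.

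On timing, item 7 of the Study Activities list (printed under Section 10.2.7) has the blocks performed with local anesthetic "versus saline after induction of general anesthesia in the operating room". Section 9.2 adds: "Randomization will occur immediately prior to the intervention". Item 6 of the same list puts randomization on the morning of surgery.

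On intraoperative analgesia, Section 9.1 describes the institutional enhanced-recovery regimen, "including the use of dexmedetomidine and ketamine infusions with as-needed fentanyl intravenous dosing". Item 10 says that a standardized local protocol is followed, but that protocol is not reproduced.

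**The concern.** The outcome window and the treatment do not start together. A total for the whole operation opens when anesthesia begins, whereas exposure begins at the injection. Under Section 9.2, randomization also comes only just before the injection. Opioid given earlier cannot respond to the block, but nothing in the endpoint definition, data list or analysis separates it out.

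At stake is how well one secondary endpoint answers its own question. A reduction expressed as a percentage of the whole-case total would understate the reduction after the block. If early doses vary between patients, they add noise that the unadjusted t-test cannot remove.

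**Working it through.** **The plan's own figure.** The only sample size stated is for 72-hour postoperative opioid (Section 12.2): mean 245 MME, SD 87, 25% reduction, alpha 0.05, power 90%, 1:1 allocation. The difference is 0.25 × 245 = 61.25 MME. By the normal approximation, n per arm = 2 × (1.960 + 1.282)² × 87² / 61.25² = 42.4, rounded up to 43, so 86 in all. This matches the plan. It contains no intraoperative opioid, so nothing below changes it. The documents give no effect size or power for the intraoperative endpoint.

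**Effect on the mean difference.** Write each patient's total as T = A + B, where A is opioid before the block and B is opioid after it starts. Assignment cannot influence A: the block has not been given, and Section 9.2 keeps the in-room anesthesia team blinded. So E(A) is equal in both arms, and the expected difference in T equals the expected difference in B. There is no bias in the mean difference and no inflation of type I error.

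**Effect on the relative reduction.** If A is a fraction f of the control-arm total, a reduction of p in B appears as p × (1 − f) in T. The documents give no f. With p = 25%, borrowed from the primary endpoint for illustration only:
- f = 0.2: 20%
- f = 0.4: 15%
- f = 0.6: 10%

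**Effect on power.** Let r = SD(A)/SD(B), with correlation ρ between A and B. Then SD(T) = SD(B) × √(1 + r² + 2ρr), and the standardized effect is divided by that root. All inputs are assumptions except the 50 per arm and the 0.05 level: a post-block effect of 0.65 SD, chosen because it gives 90% power, and a two-sided test. Power is from the noncentral t distribution.

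| r | ρ = 0: effect (SD) | ρ = 0: power | ρ = 0.3: power | ρ = −0.3: power |
|---|---|---|---|---|
| 0 (fixed pre-block dose, or none) | 0.65 | 90% | 90% | 90% |
| 0.5 | 0.65/√1.25 = 0.58 | 82% | 73% | 91% |
| 0.75 | 0.65/√1.5625 = 0.52 | 73% | 62% | 86% |
| 1.0 | 0.65/√2 = 0.46 | 62% | 51% | 78% |

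Under independence the effective sample size is 1/(1 + r²) of nominal: 80%, 64% and 50%. The loss is larger with positive correlation. If ρ is below −r/2, the total has a smaller SD than B alone and there is no loss, as at r = 0.5 with ρ = −0.3.

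**The case against.** The strongest reply is that the premise is not written down. No section says that opioid is given between induction and the block; Section 9.1 mentions only as-needed fentanyl, and the institutional protocol is not shown. That stands. The point is only that the plan neither excludes such opioid nor separates it.

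Second, a reader might infer that pre-block opioid biases the comparison or shrinks the effect under test. It does not: the t-test compares means, and the expected difference in means is untouched.

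Third, the plan promises no percentage reduction for this endpoint. The 25% target belongs to 72-hour postoperative opioid (Sections 5.2 and 12.2). That is right, and the percentages above only show how a relative figure would read if one were reported.

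Fourth, the power loss is conditional. A standardized protocol could make early dosing nearly fixed, in which case nothing is lost. With as-needed dosing, more opioid early could mean less later, and a strong enough negative correlation would make the total the more precise measure. Both are possible and the documents settle neither.

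Fifth, a whole-case total is a legitimate outcome, and perioperative analgesics are already recorded (Study Activities, item 14). This supports keeping the total as a supportive analysis. It does not align the main measure with the hypothesis in Section 12.1.2.

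Finally, a window opening when the injection is completed would be undefined for randomized patients whose block is not given or not finished, and they belong to the ITT set (Section 12.3). It would also drop opioid given after the first side is injected. Any fix has to deal with both.

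**Conclusion.** The point holds as a misalignment in one secondary endpoint. The count has no start time, the block comes after induction, and no block time is recorded, so any pre-block opioid would be included. The consequence is a smaller relative reduction and, if early dosing varies and is not strongly negatively correlated with later use, a larger SD and lower power. Under assumed pre-block SDs of 0.5 to 1.0 times the post-block SD and independence, power goes from 90% to about 82% to 62%; with a fixed pre-block dose it stays at 90%. These figures illustrate a range and do not estimate what will happen in this trial.

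The documents do not support a reading that opioid is known to be given before the block, that the test is biased or its error rate inflated, or that the primary endpoint or the 86/100 sample size is affected. This is a cheap improvement and does not threaten the trial's main conclusion.

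**What to change.** - Add block (or sham) start time to the Visit 2 items in Section 10.2.2.
- In Sections 3.1, 6.0, 10.2.2 and 12.4, define the endpoint as opioid in MME from the start of the block or sham injection to ICU arrival, which the plan already uses as time 0 for pain scores.
- For randomized patients who receive no block, start the count at the time of randomization if that is done immediately before the planned block, as Section 9.2 says; otherwise start it at the planned block time. This keeps every randomized patient in the ITT analysis. Whichever time is used must be recorded.
- Report pre-block opioid separately by arm, and keep the whole-case total as a supportive analysis.

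The cost is one extra time stamp (plus the fallback time for patients without a block), splitting doses at that time, and the wording changes. The downside is that the main figure is no longer a whole-case total. Nothing in the conduct of anesthesia changes.

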11.0 DATA HANDLING AND RECORD KEEPING

11.1 Data Collection

11.1.1 Data Collection Forms

All study data will be collected by a study team member on a standardized case report form (CRF) and stored within the university approved data collection site OnCore. Data entry into electronic format will take place on a private computer away from potential viewing by non-study personnel. The paper and electronic data will be kept in a locked office in the Department of Anesthesiology. The computer will be pass-coded and linked to a secure Anesthesia Department server to allow access only to approved study personnel. All identifiable data will be destroyed as soon as it is no longer required. De-identified

data will be retained for 7 years per UW-Madison best practices. For statistical analysis, de-identified data will be sent to biostatistician via email as a password protected encrypted zip file.

11.1.2 Data Management Software System(s)

Clinical data (including AEs, concomitant medications, and solicited events data) and clinical laboratory data will be entered into the following data management software system(s) to ensure consistent data entry and data quality. Clinical data will be entered directly from the source documents.

OnCore

The Online Collaborative Research Environment (OnCore) Clinical Trial Management Software (CTMS) will be used for this study.

OnCore is a web-based data management system that: a) ensures secure, easy data entry at multiple sites; b) integrates multiple data sources; c) provides controlled, secure access to sensitive data using role-based access control; d) provides workflow automation; and e) allows export and reporting of data for Data (and Safety) Monitoring Committee(s) and statisticians. This software provides protocol and subject management functions (e.g., subject scheduling; screening; data organization), maintains updated forms, addresses budget development, billing and fiscal management, generates summary reports, and provides essential links with research administration and electronic medical records systems. The OnCore system eases the burden of the individual researcher and unifies protocol management within research programs and across research sites, enhancing protocol integrity and regulatory compliance efforts.

The OnCore Support Team works with the investigator, statistician, and study team to ensure the relevant, applicable study data are collected and managed in a secure web-based system with restricted access using the software electronic case report forms (eCRFs). The OnCore Support Team will work with the study team to ensure the appropriate data is exported for analysis, but will not perform the analysis.

11.2 Confidentiality and Privacy

All study staff engaged in the conduct of this project have completed training on the protection of human subjects and the Health Insurance Portability and Accountability (HIPAA) Privacy Rule. In addition, all key personnel (i.e., Principal Investigator, individuals involved in identifying/recruiting subjects, obtaining informed consent, or interacting and intervening with subjects) have undergone Good Clinical Practice (GCP) training.

Information about study subjects will be kept confidential and managed according to HIPAA requirements. All subjects will sign an informed consent document and a HIPAA authorization form or a combined informed consent and HIPAA authorization form> that includes specific privacy and confidentiality rights. Study data will be maintained per federal, state, and institutional data policies.

Confidentiality will be protected to the extent possible by coding subject data and storing electronic data on password-protected anesthesiology department network computers and hard copy data in a locked study office until destruction. We will also utilize a secure information storage program OnCore. All hard copy data (source documents, signed consent forms, CRFs) will be stored in a locked study office. For statistical analysis, data will be de-identified on an excel spreadsheet that will be sent via email as a password protected encrypted zip file to the statistician.

Authorized representatives of the following groups may need to review this research as part of their responsibilities to protect research subjects: representatives of the IRB, DSMB/DSMC, and federal oversight agencies. The clinical study site will permit access to such records.

